**13c. Have there been any human deaths associated with this drug? No**

**13d. In how many humans has this drug been used previously?**

tobramycin is used routinely in patients across the country through a systemic route of administration.

**13e. If this protocol will be used in children describe any previous use of this drug with children of a similar age range. None**

**14. Do the following criteria apply? Check all that apply**

The investigation is intended to be reported to FDA as a well-controlled study in support of a new indication for use or intended to be used to support any other significant change in the labeling for the drug;

If the drug that is undergoing investigation is lawfully marketed as a prescription drug product, the investigation is intended to support a significant change in the advertising for the product;

The investigation does involve a route of administration or dosage level or use in a patient population or other factor that significantly increases the risks (or decreases the acceptability of the risks) associated with the use of the drug product.

If Not checked- explain why you believe the risk to subjects is not increased:

tobramycin has long been used in treatment and prophylactic regimens in humans; the dose used in this experiment has been proven on a cellular level in animal models to be non-toxic and effective in prophylaxis against infection.

The investigation will be conducted in compliance with the requirements for institutional review set part in part 21CFR56 and with the requirements for informed consent set forth in part 21CFR50 ; and

The investigation will be conducted in compliance with the requirements of 21CFR312.7 (Promotion and charging for investigational drugs)

**15. Is this a post-marketing study? No**

## APPENDIX: Recruitment

**1. How do you plan to identify potential subjects?**

a.  Chart Review/ Clinic Schedule Review/ Database Review from a database established for health care operations (departmental clinical database) or an Improvement Project (e.g. *Performance Improvement, Practice Improvement, Quality Improvement*).  
If you plan to obtain data from the UVa Enterprise Data Warehouse (EDW) please see option b below.

DHHS: Study team requests Waiver of Consent to identify potential subjects.

HIPAA: Allowed under Preparatory to Research if PHI to be accessed.

**IMPORTANT**

Keep in mind that PHI in the medical record may only be accessed by individuals who work under the UVa HIPAA covered entity; which means they meet one of the following criteria:

- a UVa student working in the UVa HIPAA Covered Entity\*
- a faculty or staff member in a PAID appointment in the UVA HIPAA Covered Entity\*

**b**  Review of a database that was established to keep data to be used for future research such as the CDR, departmental research database or use of data from a separate current active research protocol.

*If you plan to obtain data from the UVa Enterprise Data Warehouse (EDW) you are required to submit your request to the CDR. The CDR staff will work with the EDW to obtain the data you need.*

DHHS: Study team requests Waiver of Consent to identify potential subjects.

HIPAA: Allowed under Preparatory to Research if PHI to be accessed.

**IMPORTANT**

Keep in mind that PHI in the medical record may only be accessed by individuals who work under the UVa HIPAA covered entity; which means they who meet one of the following criteria:

- a UVa student working in the UVa HIPAA Covered Entity\*
- a faculty or staff member in a PAID appointment in the UVA HIPAA Covered Entity\*

The information from which you are obtaining potential subjects must also have an IRB protocol approval. If this item is checked, enter the IRB # below.

**IRB#**

If obtaining information from the Clinical Data Repository (CDR) insert IRB # 10797

c.  Patients UVa health care provider supplies the UVa study team with the patients contact information without patients' knowledge.

DHHS: Study team requests Waiver of Consent to identify potential subjects.

HIPAA: Allowed under Preparatory to Research if PHI will be shared by the health care provider.

**IMPORTANT**

Keep in mind that PHI may only be given to individuals who work under the UVa HIPAA covered entity; which means they meet one of the following criteria:

- a UVa student working in the UVa HIPAA Covered Entity\*
- a faculty or staff member in a PAID appointment in the UVA HIPAA Covered Entity\*

d.  Patient obtains information about the study from their health care provider. The patient contacts the study team if interested in participating. (Health care provider may or may not also be a member of the study team)

DHHS: NA

HIPAA: Allowed under Health Care Operations

If this choice is checked, check 3d-INDIRECT CONTACT below.

e.  Potential subjects will not be directly identified. They will respond to an advertisement such as a flyer, brochure etc.

If this choice is checked, check 3d- INDIRECT CONTACT below.

DHHS & HIPAA: NA

f.  Potential subjects have previously signed a consent to have their name in a registry/database to be contacted for future studies of this type.

**IRB# of registry/ database:**

DHHS & HIPAA: NA

**If item # a, b or c is checked above and if this protocol involves the use of protected health information do you confirm the following to be true? yes**

- The use or disclosure is sought solely to review protected health information as necessary to prepare the research protocol or other similar preparatory purposes.
- No PHI will be removed from the UVa covered entity.
- The PHI that the researcher seeks to use or access is necessary for the research purposes.

## 2. How will potential subjects be contacted?

To "contact" a potential subjects refers to the initial contact you plan to take to reach a potential subject to determine if they would be interested in participating in your study. This may include direct contact by such methods as by letter, phone, email or in-person or indirect contact such as the use of flyers, radio ads etc.

If your study involves more than one group of subjects (e.g. controls and cases or subjects and caregivers) note below which groups are being contacted by the given method.

Check the methods below you plan to utilize:

a.  Direct contact of potential subjects by the study team via letter, phone, direct e-mail. Members of study team ARE NOT health care providers of patients. Information will not be collected from psychotherapy notes.

Note: Letter, phone, direct email scripts must be approved by IRB prior to use.

See [IRB-HSR Website](#) for templates.

DHHS/HIPAA: Study team requests a Waiver of Consent and Waiver of HIPAA Authorization to contact potential subjects.

IMPORTANT:

Keep in mind that if PHI was collected during the identification phase that contact with potential subjects may only be performed by individuals who work under the UVa HIPAA covered entity; which means they meet one of the following criteria:

- a UVa student working in the UVa HIPAA Covered Entity\*
- a faculty or staff member in a PAID appointment in the UVA HIPAA Covered Entity\*

b. Potential subjects will be approached while at UVa Hospital or Health Clinic by a person who is NOT a member of their health care team. Information will not be collected from psychotherapy notes.

DHHS & HIPAA: Study team requests a Waiver of Consent and a Waiver of HIPAA Authorization to contact potential subjects.

IMPORTANT:

Keep in mind that contacting individuals in a clinical setting may only be performed by individuals who work under the UVa HIPAA covered entity; which means they meet one of the following criteria:

- a UVa student working in the UVa HIPAA Covered Entity\*
- a faculty or staff member in a PAID appointment in the UVA HIPAA Covered Entity\*

You should share the following information with the potential subject:

- Your name
- Who you are: physician, nurse etc. at the University of Virginia.
- Why you want to speak with them
- Ask if you have their permission to explain the study to them
- If asked about how you obtained their information use one of the following as an option for response.

- DO NOT USE THIS RESPONSE UNLESS YOU HAVE OBTAINED PERMISSION FROM THEIR UVa PHYSICIAN: Your doctor, Dr. insert name wanted you to be aware of this research study and gave us permission to contact you.
- We obtained your information from your medical records at UVa.
- Federal regulations allow the UVa Health System to release your information to researchers at UVa, so that we may contact you regarding studies you may be interested in participating. We want to assure you that we will keep your information confidential.

- IF THE PERSON SEEMS ANGRY, HESITANT OR UPSET, THANK THEM FOR THEIR TIME AND DO NOT ENROLL THEM IN THE STUDY. YOU MAY ALSO REFER THEM TO THE IRB-HSR AT [name].

c. X Direct contact of potential subjects by the study team by approaching in person at UVa or via letter, phone, direct e-mail. Members of study team contacting potential subjects ARE health care providers of patients.

If you are not approaching them in person but using a letter, phone call or direct email please note that the letter, phone, direct email scripts must be approved by IRB prior to use.

See [IRB-HSR Website](#) for templates.

DHHS: Study team requests a Waiver of Consent to contact potential subjects

HIPAA: Allowed under Health Care Operations.

d.        Indirect contact (flyer, brochure, TV, broadcast emails, patient provided info about the study from their health care provider and either the patient contacts study team or gives their healthcare provider permission for the study team to contact them.)

The indirect method used (flyer, brochure, TV, broadcast emails) must be approved by the IRB prior to use. The IRB does not need to review any type of script to use when the potential subject responds to the indirect method.

DHHS & HIPAA: NA

e.        Potential subjects are not patients. The study does not include obtaining subjects health information. Subjects will be contacted directly via email, phone, letter or presentation in group setting with consent then obtained individually in a private setting.

If you are not approaching them in person but using a letter, phone call or direct email please note that the letter, phone, direct email scripts must be approved by IRB prior to use.

See [IRB-HSR Website](#) for templates.

DHHS: Study team requests a Waiver of Consent to contact potential subjects

HIPPA: NA

3. Will any additional information be obtained from a potential subject during "prescreening"?  
NO

4. Do you plan to ask the subjects to do anything, other than answering questions, for the study prior to signing a consent? NO

**5. How will the consenting process take place with either the prospective subject, the subject's legally authorized representative or parent/legal guardian of a minor ( if applicable)?**

HIPPA:

If the individual, obtaining consent, works under the HIPAA Covered Entity consenting is covered under Health Care Operations.

If the individual obtaining consent does not work under the HIPAA covered entity, HIPAA does not apply.

Subjects who are being treated for open fractures at University of Virginia, who agree to participate in the study will be asked to sign an informed consent at the hospital. Subjects will be given ample time to go over the informed consent, and an opportunity will be provided to ask questions. Subjects are also allowed to discuss with family and relatives before they sign the consent. Anywhere, from one hour to one week may pass between written consent and initiation of study procedures.

If subject is unresponsive or intubated, and cannot adequately answer the questions and if it is determined that the patient's level of cognition is not likely to change before surgery, a legally authorized representative (LAR) will be approached for proxy consent. Guidance will be provided to assist the LAR in making consent decision. They will be advised to base the decision on the patient's expressed wishes, or, what they believe the patient would have desired under the circumstances of the injury. His or her beliefs and values. When participant regains capacity to consent during the study period, the participant will be re-consented using standard consenting procedures as described below.

**6. Will subjects sign a consent form for any part of the study? NO**

**7. Will the study procedures be started the same day the subject is recruited for the study?**

This will depend on the patient's clearance status for the OR. Often, some patients will have to be resuscitated in an ICU setting prior to going to the OR for definitive treatment and wound closure. Also, some wounds cannot be closed during the index procedure and they will have to be taken back to the OR for further treatment and wound closure.

**► IF YES, explain in detail why the subject cannot be given more time to make a decision to consent.**

Open fractures are surgical emergencies that need to be irrigated/debrided and stabilized and possibly closed as quickly as possible.

**► IF YES, explain in detail what will be done to assure the potential subject has enough time to make an informed decision.**

The study will be explained to the patient before the patient is brought back to the OR and the patient will have adequate time to ask questions and discuss his or her eligibility in the study with family and friends in the preoperative holding area or in the respective room.

**8. Is there the potential to recruit economically or educationally disadvantaged subjects, or other vulnerable subjects such as students or employees? YES**

**IF YES, what protections are in place to protect the rights and welfare of these subjects so that any possible coercion or undue influence is eliminated?**

Subjects will be told that their participation is totally voluntary. If they are employees of UVA, they will be assured that their decision to participate or not will not affect their job. If they are students, they will be assured that their decision will not in any way affect their grades.

**9. Do you need to perform a “dry run” of any procedure outlined in this protocol? NO**

## APPENDIX: Privacy Plan for Studies With Consent/HIPAA Authorization

**1. Answer the questions below (1A-1G) to describe the plan to protect the data from improper use and disclosure.**

**1A. Will any HIPPA identifiers be collected by the UVa study team ? YES**

**INSTRUCTIONS:**

Answer YES to any item below that will be written down/kept/recorded in any way.

If you answer NO to all items it means you would never be able to go back and obtain any additional data about an individual.

YES	NO	HIPAA Identifier
		1. Name
		2. Postal address information, other than town or city, state, and zip code
		3. Age or Date of Birth if over the age of 89
		4. Telephone numbers
		5. Fax numbers
		6. Electronic mail addresses
		7. Social Security number
		8. Medical Record number
		9. Health plan beneficiary numbers
		10. Account numbers
		11. Certificate/license numbers
		12. Vehicle identifiers and serial numbers, including license plate numbers
		13. Device identifiers and serial numbers
		14. Web Universal Resource Locators (URLs)
		15. Internet Protocol (IP) address numbers
		16. Biometric identifiers, including finger and voice prints
		17. Full face photographic images and any comparable images
		18. Any other unique identifying number, characteristic, code that is derived from or related to information about the individual (e.g. initials, last 4 digits of Social Security #, mother's maiden name, first 3 letters of last name.)
		19. Any other information that could be used alone or in combination with other information to identify an individual. (e.g. rare disease, study team or company has access to the health information and a HIPAA identifier or the key to the code)

**1A(1)► If you checked any item above, list the HIPAA identifiers that will be kept with the data in the same location (e.g. on the same electronic drive (e.g. F or O drive) or in the same paper file with the data).**

**INSTRUCTIONS : If you checked # 19 above:** If the key to the code ( subject # 1= John Smith) will be kept in the same location as the data, list item # 19 below.

Medical Record Number

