#### **Subjects- see below**

- 1. Provide target # of subjects (at all sites) needed to complete protocol.** 133
- 2. Describe expected rate of screen failure/ dropouts/withdrawals from all sites.**

Approximately, 20% of subjects will be lost to follow up

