**3. Provide a justification for the sample size used in this protocol.**

A sample size analysis was completed for different alpha and power levels. A one-sided test for proportions was chosen to compare the baseline (no treatment) group to the hypothesized proportion (treatment group); based on historical data, we assumed that the no treatment group would have a 10% infection rate, and the treatment group would have a 1% infection rate. Using an alpha of 0.05 and power of 70%, we would need to have 60 patients in each group.

With an expected accrual rate of 65 patients per year, we would expect to enroll 130 patients in two years. In order to maintain the sample size needed to ensure statistically valid results, we would want to enroll approximately 133 patients over the study period to end up with at least 120 patients in the analysis.

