### Biomedical Research

**1. What will be done in this protocol?**

Patients who present with open fractures to UVA Health System will be approached for participation in the study. After obtaining Informed consent, subjects will be randomized to Antibiotic Arm (experimental) or Placebo. Administration of the local antibiotic in this study is being done solely for answering a research question on the efficacy of the antibiotic tobramycin in decreasing the risk and rate of infection.

Subjects will be randomized to the experimental group, who will be injected locally at the wound cavity (i.e. fracture site, surrounding soft tissue which include muscle, and subcutaneous space) with 80mg/40mL of tobramycin after wound closure, and placebo group who will be injected locally with 40 mL 0.9% NS after wound closure. Systemic antibiotic will not be withheld and will be done along side the local injection of tobramycin. If patient returns to the OR for repeat debridement procedures, the injection will be repeated. If patient returns to the OR for repeat debridement procedures, the injection will be repeated. The second injection will only be given if the subject undergoes a repeat procedure, and will be given two days later than the first injection. By this time, serum tobramycin levels would have normalized, given the low doses and time interval. . Dose volume will not be adjusted because the safety of this antibiotic assumes that the patient weighs at least 16 kg, and any patient 18 years or older will weigh more than that. While systemic antibiotic treatment is standard of care, animal studies and early clinical case series data indicated that injection of aqueous aminoglycoside after wound closure locally could be a highly effective technique for wound infection prophylaxis[1]. In this study protocol, other aminoglycosides (eg. Gentamycin) will be allowed as part of standard systemic prophylaxis.

Follow up data will be collected at 2 weeks, 6 weeks. Clinical data will be collected from medical records

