**2. List the procedures, in bullet form, that will be done for RESEARCH PURPOSES as stipulated in this protocol.**

- Medical record review at baseline and all subsequent study weeks up to 1 year after surgery
- Randomization to Antibiotic ( tobramycin) arm or Placebo before surgery by clinical pharmacy program at UVA.
- Experimental group will have the close wound injected with 80 mg/40mL of tobramycin at the END of surgery
- Control group will have 40 mL 0.9%NS injected into the closed wound at the end of the case
- Follow up at 2 and 6 weeks at the clinic. *These visits to the clinic will coincide with the follow up as in standard of care for open fracture management.*

**3. Will you be using data/specimens in this study that were collected previously, with the use of a research consent form, from another research study? NO**

**4. Will any of the procedures listed in item # 2 have the potential to identify an incidental finding? This includes ALL procedures, assessments and evaluations that are being done for RESEARCH PURPOSES that may or may not be considered investigational. yes**

► IF YES, check one of the following two options:

The examination(s) utilize(s) the same techniques, equipment, etc., that would be used if the subject were to have the examination(s) performed for clinical care. **There exists the potential for the discovery of clinically significant incidental findings.**

- The PI takes full responsibility for the identification of incidental findings:
- The PI will inform the subjects verbally of all incidental findings that are of clinical significance or are of questionable significance.
- A follow-up letter describing the finding should be provided to the subject with instructions to either show the letter to their PC or if the subject has no PCP, the subject should be instructed to make an appointment at UVa or at the Free Clinic.

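### The 6-week infection outcome is collected passively: the plan has no step to contact subjects who miss the visit or to ask about care elsewhere, although it expects 20% loss.

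*Combined protocol and SAP*

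**What the plan says.** All references are to the combined protocol and SAP.

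- **Source of outcome data.** Biomedical Research, item 1, sets data collection at 2 and 6 weeks and adds: "Clinical data will be collected from medical records". Item 2 places both follow-ups at the clinic and says: "These visits to the clinic will coincide with the follow up as in standard of care for open fracture management". The same item has the medical record reviewed up to 1 year after surgery.
- **Endpoint.** Statistical Considerations, item 2, defines the primary outcome as infection within 6 weeks. A major infection is a return to the operating room for irrigation and debridement. A minor infection is documented cellulitis or superficial infection with oral antibiotics.
- **Expected loss.** Subjects, item 2: "Approximately, 20% of subjects will be lost to follow up".
- **Sample size.** Statistical Considerations, item 3: "Using an alpha of 0.05 and power of 70%, we would need to have 60 patients in each group". About 133 are to be enrolled "to end up with at least 120 patients in the analysis".
- **Identifiers.** In the Privacy Plan appendix, items 1A and 1D(2), the row "4. Telephone numbers" is answered NO, as are postal address and e-mail. The medical record number is answered YES and is kept with the data.

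No section describes a telephone contact, tracing of a missed visit, or a request for records from another provider.

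**The concern.** A subject who does not come back at 6 weeks contributes an outcome only if the study hospital's chart happens to show one. Cellulitis treated with oral antibiotics can be managed by a local doctor or an emergency department and leave no entry in that chart. Such a subject either drops out of the analysis or is counted as uninfected. Adverse-event reporting is not a backstop, because section 3.1 of the Data and Safety Monitoring Plan records only events deemed related or possibly related to the study.

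The trial has little room for this. At the plan's own rates, 60 per group gives 60 × 0.10 + 60 × 0.01 = 6.6 expected infections in total, so one missed infection is about 15% of the events (1/6.6). Planned power is only 70%.

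**Working it through.** **Inputs.** One-sided alpha 0.05, power 70% and 60 per group come from Statistical Considerations, item 3, which also gives the rates: "we assumed that the no treatment group would have a 10% infection rate, and the treatment group would have a 1% infection rate". Equal allocation is inferred from the equal group sizes. Enrolment is 133 and the analysis target 120 (same item). Loss is 20% (Subjects, item 2). The documents give no share of lost subjects who could be recovered and no share of infections that would go unseen, so both are assumed and shown as ranges.

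**1. Reproduce the plan's figure.** Pooled normal formula without continuity correction, with mean rate (0.10 + 0.01)/2 = 0.055:

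n = {[1.645 × √(2 × 0.055 × 0.945) + 0.524 × √(0.10 × 0.90 + 0.01 × 0.99)] / 0.09}²
= {[0.530 + 0.166] / 0.09}² = 59.8, so 60 per group. This matches the plan. Power at 60 is 70.1%.

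**2. Apply the plan's own loss.** 133 × 0.80 = 106.4 analysed, or 53.2 per arm. Power = Φ[(0.09 × √53.2 − 0.530)/0.316] = Φ(0.399) = 65.5%. Enrolling 133 to analyse 120 allows a loss of only 1 − 120/133 = 9.8%. Keeping 120 at 20% loss needs 120/0.80 = 150 enrolled.

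**3. Recover part of the lost.** Lost: 133 × 0.20 = 26.6, about 27.

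| Share recovered (assumed) | Analysed | Power |
|---|---|---|
| 0% | 106.4 | 65.5% |
| 25% | 113.0 | 67.8% |
| 50% | 119.7 | 70.0% |
| 75% | 126.3 | 72.1% |
| 100% | 133.0 | 74.0% |

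**4. Infections unseen and counted as none**, in equal proportion in both arms, 60 per group:

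| Share unseen (assumed) | Observed rates | Absolute difference | Power |
|---|---|---|---|
| 0% | 10% vs 1% | 9.0 points | 70.1% |
| 10% | 9.0% vs 0.9% | 8.1 points | 65.8% |
| 20% | 8.0% vs 0.8% | 7.2 points | 61.1% |
| 30% | 7.0% vs 0.7% | 6.3 points | 56.0% |

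The ratio of the two rates stays at 10 throughout. Only the absolute difference and the power shrink.

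**5. Does it matter how lost subjects are handled?** If all 133 stay in the analysis and every infection among the lost 20% is counted as none, the rates are 8.0% vs 0.8% at 66.5 per arm and power is 65.0%. This is close to the 65.5% obtained by dropping them.

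All these are planning-formula figures. With so few events, a one-sided Fisher exact test has less power (55.6% at 60 per group, 46.5% at 53), so the differences between rows matter more than the levels.

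**The case against.** The strongest reply is that this is a pragmatic trial built on routine care, and that several stronger readings go further than the documents allow. Five of these should be set aside.

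- **That the privacy table bars contact.** A reader might infer this from the NO against telephone, address and e-mail. The table governs what the study team records. Its instruction says that going back for more data is ruled out only if every item is NO, and the medical record number is YES. The later limit on contacting subjects (Privacy Plan, item 3) applies after the study is closed.
- **That infections after a missed visit are never found.** Record review to 1 year would show an infection treated at the study hospital, including a return to its operating room. Ability to attend follow-up is also an inclusion criterion.
- **That one call would settle the outcome.** The minor-infection definition requires documentation, which a subject's own report does not supply.
- **That minor infections are half of the events.** The plan names two categories and gives no split.
- **That the comparison is biased.** Subject and surgeon are blinded, so missed infections should be similar in proportion across arms.

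Three further points limit the size. The fall from 70% to 65.5% comes from the conflict between 20% loss and the 9.8% implied by 133 and 120, which needs reconciling in any case. The 10% control rate rests on historical data of unstated ascertainment. If those data came from routine charts, the rate already contains the same under-detection and step 4 would count it twice. The consent pages and case report forms are not available here and might already allow contact or ask about outside treatment. The identifier table also covers the UVA team only.

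What remains is that Biomedical Research, items 1 and 2, set out the follow-up and contain no retrieval step, while the plan itself expects one subject in five to be lost.

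**Conclusion.** The concern holds as a gap in data collection. The plan has no procedure for learning the 6-week status of non-attenders, or for finding infections managed elsewhere and absent from the study hospital's chart. Minor infections treated with oral antibiotics are the likeliest to be missed in this way.

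With 20% loss and no retrieval, planning-formula power is 65.5% against the intended 70%. About half of the roughly 27 lost subjects would have to be recovered to reach 120 with no extra enrolment, and recovery of 25% to 75% gives about 68% to 72%. If 10% to 30% of infections went unseen, power at 60 per group would be about 66% to 56%, unless the historical 10% already reflects that. The recovery and unseen shares are assumptions. The sample-size figures and the 20% loss are the plan's own. The expected harm is lost power and a smaller absolute difference. This is a worthwhile, inexpensive improvement and does not invalidate the trial.

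**What to change.** In Biomedical Research, item 2:

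1. Add a scripted telephone contact at 6 weeks, made by existing study staff who do not know the arm, for every subject without a 6-week visit. Ask whether a wound infection was diagnosed, whether oral antibiotics were given for the wound, and whether the subject returned to any operating room.
2. Ask the same questions at the 6-week visit, so that attenders treated elsewhere are also found.
3. Confirm each positive answer from the outside record, so that the documentation requirement in Statistical Considerations, item 2, is met.
4. Change the telephone row in Privacy Plan items 1A and 1D(2) only if numbers will be recorded outside the chart, and check that the consent form covers the call and the record request.
5. Reconcile the 20% loss with the 133-to-120 calculation.

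The cost is about 27 subjects to call over two years (roughly one a month), possibly with repeat attempts, some outside-record requests, and a consent and privacy edit. The alternative of enrolling 150 means 17 more patients, about a quarter of a year at the planned 65 per year, and would not find infections treated elsewhere.
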